2.0 OBJECTIVES AND SCIENTIFIC AIMS

Primary Objective:

To investigate the feasibility, applicability, and reproducibility of a novel hyperspectral camera system in perfusion and oxygenation detection in healthy volunteers.

Secondary Objectives:

- To explore the effect of occlusion-reperfusion of the brachial artery on cutaneous blood flow as assessed by a hyperspectral camera system.
- To explore the effect of applying topical vasoconstrictors / vasodilators on the cutaneous blood flow as assessed by a hyperspectral camera system.
- Selection of relevant spectral bands for oxygenation and perfusion detection.

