An emerging technique is hyperspectral imaging, which is capable to detect the scattering and absorption of light delivered to the tissue, caused by inhomogeneity of biological structures, such as haemoglobin, fat or water [11]. In vivo real-time imaging of the perfusion is currently not possible, however snapshot imaging was used to evaluate oxygen levels in the retina, which was quite complex, especially the part of data processing [12, 13]. Recently, a novel hyperspectral imaging camera (Quest Medical Imaging BV, Middenmeer, The Netherlands) has become available as prototype. This device allows non-invasive measurement of skin blood flow, oximetry and (vascular) anatomy, only based on the endogenous contrast of the tissue. Therefore it could be used to obtain non-invasively information about the (superficial) anatomical structures and moreover to measure the microvascular condition.

However the capability of this device to pick up physiological changes is unknown. To validate this hyperspectral camera system (HCS) for measuring skin blood flow and vascular anatomy the following study is proposed:

- Measurement of forearm skin blood flow before, during and after occlusion of the brachial artery;
- Measurement of local changes in skin blood flow after applying a local capsaicin-based cream (local vasodilator);

Read outs from the HCS after local application of capsaicin-based cream will be compared to measurements of an untreated area of the forearm. Furthermore, the changes in these measurements will be evaluated over time..

Hyperspectral camera system:

Hyperspectral imaging is a non-invasive optical technique, using halogen light as a light source, which is also widely used in commercially available light sources. Halogen light could produce some heat, however imaging will be performed on a distance of 50 centimetres. The technology used in this camera, is partially comparable to the technology used in Diffuse Reflectance Spectroscopy, which has been used in diverse clinical studies in the Netherlands Cancer Institute without reporting of any side effects during the measurements [17, 18].

Summary of findings from non-clinical studies

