The HCS is recently developed and is one of the first camera systems which is expected to create two-dimensional imaging of tissue perfusion based on endogenous tissue contrast, which is far beyond the current state of the art. This study will be the first clinical study in human volunteers and no findings of earlier performed non-clinical studies are available.

We expect no side effects, because this technique only uses halogen light as light source, which is also widely used in commercially available light sources. The sensors used in this camera, are partially comparable to the sensors used in Diffuse Reflectance Spectroscopy. In the Netherlands Cancer Institute good results in tissue characterization and tumor detection were achieved, however this technique is only capable to perform point measurements and could therefore not be used during surgery in the future. They also showed that no side effects occurred during and after the measurements [17, 18].

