4.0 OVERVIEW OF STUDY DESIGN/INTERVENTION

4.1 Design

This study is a non-therapeutic open observational trial, which evaluates the feasibility of the hyperspectral camera system (a non-significant risk device) in evaluation of the tissue perfusion and oxygenation in different circumstances. The exploratory aim of this study is to select relevant spectral bands for oxygenation and perfusion detection, which can be used for further camera development and consequently in clinical practice. Eight healthy volunteers, without any medication use and without any relevant medical history will be included in this study. Subjects will be enrolled following confirmation of study eligibility (section 5.0) which will be checked at baseline. Reproducibility will be validated by performing the following HCS measures:

- Basal blood flow
- Blood flow upon occlusion-reperfusion brachial artery
- Blood flow after applying capsaicin-based cream
- The room temperature, which could influence the skin perfusion will also be measured.

For the secondary endpoints, hyperspectral measures of:

- basal blood flow / oximetry
- blood flow /oximetry upon occlusion-reperfusion brachial artery
- Blood flow / oximetry after applying capsaicin-based cream

Reproducibility will be validated by the HCS measure only, at both time points that the HCS is used.

Explorative endpoint:

The explorative endpoint of the study is to see if a selection of spectral bands, specific for tissue perfusion and oxygenation (selected after data processing of above mentioned measurements) can be achieved.

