11.0 BIOSTATISTICS

Primary study parameter(s)

Reproducibility is measured by performing the measurements on two different days in the same study population. Sample T-tests will be used for comparison of the perfusion

measured by the HCS system and room temperature in the eight recruited human volunteers. The intra-subject variability over the two measurement moments will be established by calculation of the coefficient of variation.

Secondary study parameter(s)

For spectral measurements no specific statistical analysis is performed. It is mainly a part of data processing as described in the study design protocol section 4.0.

Leiden University Medical Center (LUMC) is utilizing their own protocol under their own regulatory body oversight, and conducting separate but similar protocols. LUMC data will be pooled with our data for analysis.

The PI of this study will be sharing de-identified data with an external collaborator at Leiden University Medical Center for the purpose of data analyses. Anonymized images taken from the hyperspectral camera will be electronically sent to Quest Medical Imaging for analysis.

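### Reproducibility rests on a t-test of unstated type, which can detect only a mean shift, and a coefficient of variation with no stated formula or interval

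*Combined protocol and SAP*

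**What the plan says.** The primary objective in Section 2.0 is "To investigate the feasibility, applicability, and reproducibility of a novel hyperspectral camera system in perfusion and oxygenation detection in healthy volunteers". Section 4.1 adds "Reproducibility will be validated by the HCS measure only, at both time points that the HCS is used", but no statistic.

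The analysis is in Section 11.0, under the primary study parameter. It first defines reproducibility as repeat measurement of one group of subjects on separate days. It then says "Sample T-tests will be used for comparison of the perfusion" "measured by the HCS system and room temperature in the eight recruited human volunteers", and finally "The intra-subject variability over the two measurement moments will be established by calculation of the coefficient of variation". No test type, contrast, alpha, CV formula, interval or acceptance limit is stated there or in Sections 4.1, 7.0 or 9.0.

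Section 11.0 also says "LUMC data will be pooled with our data for analysis". The LUMC protocol is listed as Appendix 3, but its text and its sample size are not in the material available.

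On room temperature, Section 7.0 describes two similar study days, with temperature taken before the measurements. The Section 9.0 table marks it at Visit 1 only.

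**The concern.** A t-test asks whether two means differ. Reproducibility asks how far one subject's two values lie apart. A noisy device with no average drift will usually give a non-significant test. A very precise device with a trivial drift may give a significant one. The test result therefore does not rank devices by reproducibility.

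The CV does answer the question, but three things about it are open: which formula is used, how uncertain the result is, and whether a day-to-day shift is counted in it. Two analysts could report different CVs from the same eight pairs. A bare figure from eight pairs would also look much firmer than it is. Section 4.1 says the results are to guide further camera development and later clinical use, so the number is likely to be carried forward.

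**Working it through.** **Inputs.** From the documents: 8 volunteers (Sections 1.0 and 4.1) and two study days 3 to 28 days apart (Section 7.0). The documents give no alpha, expected CV, shift of interest or precision target, so there is no planned figure to reproduce. Assumed here: two-sided alpha 0.05, no dropout, a true shift of 5% of the mean, and within-subject CVs (CVw) of 2% to 20%.

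**1. Paired t-test power.** The SD of the day difference is √2 × CVw. The noncentrality is 5 × √8 / (√2 × CVw) = 10 / CVw, with CVw in percent. There are 7 degrees of freedom (df) and the critical value is 2.365.

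| CVw | Noncentrality | Power for a 5% shift |
|---|---|---|
| 2% | 5.0 | 98.9% |
| 5% | 2.0 | 40.8% |
| 10% | 1.0 | 14.0% |
| 20% | 0.5 | 7.2% |

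The noisier the measurement, the less likely the test is to report a difference.

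**2. No shift at all.** In 100,000 simulated studies per setting, the paired test was non-significant in 94.9% to 95.1% of them at each within-subject SD tried, from 5% to 60% of the mean. Over that range the intraclass correlation falls from 0.94 to 0.10 (assumed between-subject SD 20%). Conversely, a 2% shift at a CVw of 1% (noncentrality 2 × √8 / (√2 × 1) = 4) is significant 93% of the time.

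**3. Precision of the CV.** The approximate 95% limits are the estimate times √(df/χ²). With 7 df these are √(7/16.013) = 0.661 and √(7/1.690) = 2.035. An observed 10% then gives 6.6% to 20.4%.

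**4. Effect of pooling.** Take df as pairs minus sites. If LUMC contributed 8 subjects (assumed), df = 16 − 2 = 14, the factors are 0.732 and 1.577, and 10% gives 7.3% to 15.8%. If it contributed 16 (assumed), df = 24 − 2 = 22, the factors are 0.773 and 1.415, and 10% gives 7.7% to 14.2%.

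**5. Choice of formula.** The CV of two values is |difference| / (√2 × mean). Without a shift, its average over subjects is about √(2/π) = 0.798 of the true CV, which is 0.080 for a true 0.10. The root mean square of the same values gives 0.101 in simulation.

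**6. Matching the interval to the formula.** The root mean square includes any mean shift. With a 7 df interval at CVw 5%, its simulated coverage of the within-subject CV falls to 0.87 under a 5% shift and 0.34 under a 10% shift. The SD of the percentage differences divided by √2 removes the shift, and its 7 df interval keeps coverage of about 0.93 to 0.95. For example, an SD of differences of 14.14% gives 14.14/√2 = 10%.

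**7. The shift itself.** At a CVw of 10%, the 95% half-width of the mean day difference is 2.365 × 14.14 / √8 = 11.8 percentage points.

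**The case against.** The best defence is that the plan gives each tool its proper job: the t-test is for comparison, and the CV is for intra-subject variability. A shift check beside a within-subject CV is a sensible pair. The study is small and exploratory, and Section 3.0 says "no findings of earlier performed non-clinical studies are available", so there was little basis for a margin or an expected CV. All of this stands, and it rules out several stronger readings:

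- *A reader might infer that a non-significant t-test will be taken as proof of reproducibility.* The plan states no such rule.
- *A reader might infer an unpaired test, or a test of perfusion against room temperature.* The wording leaves both open. However, repeat days in the same subjects and the intra-subject label point to a paired comparison between days, and perfusion and temperature are in different units.
- *A reader might infer that only a point estimate of the CV is planned.* That would rest on silence: no interval is stated, but none is excluded. Reference 16 in the list concerns choosing a sample size for CV accuracy. It is not cited in the body, so it settles nothing, but it suggests that precision may have been considered.
- *A reader might apply the factor of two to the final pooled result.* It applies to eight pairs, and the LUMC sample size is unknown.

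The defence does not supply the test type, the contrast, the formula or the interval.

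**Conclusion.** The point holds as a weakness of method and specification that is cheap to repair. Even read as a paired day comparison, the t-test cannot show reproducibility: its power against an assumed 5% shift falls from 99% to 7% as the CV rises from 2% to 20%. The CV is the right measure, but from eight pairs it is uncertain by about 0.66 to 2.04 times, and the choice of formula alone can move it by about 20%.

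The power figures rest on the assumed alpha, shift and CVs. The interval factors depend only on the number of pairs and on roughly normal differences. Nothing here shows that eight subjects is the wrong number, or that a formal agreement test or pass/fail limit is needed. Because the visits are days apart, the CV reflects device noise and physiological variation together and should be described as between-day.

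**What to change.** Replace the t-test and CV sentences in Section 11.0 with text such as:

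> For each HCS condition, the primary reproducibility measure is the between-day within-subject CV. It is the SD across subjects of the day 2 minus day 1 difference, expressed as a percentage of the subject's two-day mean, divided by the square root of 2. A 95% chi-square interval on pairs minus one degrees of freedom is given (7 for eight pairs; when pooled, pairs minus number of sites, with the day difference removed within site). Where values are near zero, the within-subject SD in original units is used instead. The paired mean difference, day 2 minus day 1, with its 95% CI is reported beside it as the check for systematic shift, which this CV excludes. Any t-test is paired, day 1 versus day 2; non-significance is not evidence of reproducibility. Results are descriptive.

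State also that perfusion and room temperature are each compared between days, not with each other. Reconcile the Section 9.0 table, which marks room temperature at Visit 1 only, with Section 7.0, so that the Visit 2 reading exists. Bland-Altman limits of agreement are optional.

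The cost is wording in one section, one table correction and slightly more analysis. The camera data are already scheduled at both visits. The downside is that the CV will appear with a visibly wide interval.

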1.0 PROTOCOL SUMMARY AND/OR SCHEMA

This is an open observational study being done to test the feasibility and reproducibility of a hyperspectral camera system (HCS) in human skin perfusion. Oxygenation detection will be evaluated, resulting in selection of spectral bands, which could be used in clinical practice. Eight healthy volunteers will be included.

Feasibility and reproducibility of a hyperspectral camera system in human skin perfusion and oxygenation detection will be evaluated, resulting in selection of spectral bands, which could be used in clinical practice.

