7.0 ASSESSMENT/EVALUATION PLAN

Subjects will participate on 2 similar study days, separated by a minimum of 3 days and maximal 28 days. Measurements will be assessed by the HCS and will take maximum 2 hours.

Pre-treatment evaluation (after study consent and registration of volunteers):

- Medical history review
- Weight

Once eligibility is confirmed:

- Blood pressure
- Heart rate
- Room temperature

On study procedures to be followed:

- 1) The volunteer is installed at the test location (Pre-surgical Center, M-6) at the main hospital

- 2) Before starting the measurements, the blood pressure, heart rate and room temperature are measured to establish the baseline characteristics.
- 3) The volunteer is asked to stretch both forearms near to each other in sitting position.
- 4) The blood flow is measured by the HCS at baseline on both forearms (Total field of view: max. 10 x 10 cm)
- 5) After baseline measurements the flow is measured on either the right or left forearm during five minutes occlusion (a blood pressure cuff will be used) of the right brachial artery and during five minutes of reperfusion after occlusion.
- 6) After taking these measurements, there is a short break of 5 minutes, to save all measurements.
- 7) Local capsaicin-based cream is administrated on the same forearm on an area of 3 x 3 cm, on a distance of 5 cm under the radiocarpal joint.
- 8) 30 minutes after application of the crème, crème is removed from the skin.
- 9) For obtaining optimal flare, 20 minutes after removing the crème, the perfusion is measured by HCS for 5 minutes.
- 10) Region with administrated local capsaicin-based cream is compared to control regions located on the same forearm,
- 11) After 10 minutes the procedure is finished.

Concomitant medications and alcohol/caffeine consumption

The use of the following concomitant medications is prohibited: no prescription medications, over-the-counter (OTC) medications, vitamin, herbal and dietary supplements will be permitted within 14 days prior to study drug administrations, or less than 5 half-lives (whichever is longer, and during the course of the study. The following exceptions are applied:

- paracetamol (up to 4 g/day).
- Other exceptions will only be made if the rationale is discussed and clearly documented by the investigator

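### The CV is the only stated measure of day-to-day variability, and it may be inflated for occlusion-phase readings if these are low and error does not shrink with the signal

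*Combined protocol and SAP*

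**What the plan says.** Reproducibility is part of the primary objective (Section 2.0). Section 11.0 sets out the design, "Reproducibility is measured by performing the measurements on two different days in the same study population", and the summary of intra-subject variability over the two days, which is to be established by "calculation of the coefficient of variation". The only other analysis named for the primary parameter is a t-test of unspecified type: "Sample T-tests will be used for comparison of the perfusion". It compares mean levels and does not measure variability. No within-subject SD, repeatability coefficient, limits of agreement or intraclass correlation appears anywhere in the document.

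The data are small: "Eight healthy volunteers will be included" (Section 1.0), and "Subjects will participate on 2 similar study days, separated by a minimum of 3 days and maximal 28 days" (Section 7.0).

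Section 4.1 lists the flow measures used to validate reproducibility: basal flow, "Blood flow upon occlusion-reperfusion brachial artery", and flow after capsaicin cream. Under step 5 of Section 7.0, readings are taken "during five minutes occlusion" and then during five minutes of reperfusion.

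Section 11.0 does not say whether the CV is calculated by condition or pooled, on which camera output and in what units, over which time window, by which formula across volunteers, or against what acceptance limit.

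**The concern.** A CV is a sound sole summary of repeatability when the SD rises and falls with the mean. Nothing in the plan supports or checks that, and Section 3.0 says there are no earlier findings for this device. Arterial occlusion is one of the two provocations in the study and is there to reduce flow. If the reading falls and some of the error does not fall with it, the denominator shrinks faster than the numerator.

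A reader comparing CVs across conditions could then judge the occlusion phase less reproducible than baseline although its absolute error is the same or smaller. That would weaken the primary reproducibility conclusion for one provocation, in a study whose results are meant to guide further camera development (Section 4.1).

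**Working it through.** The documents give no SD, expected CV, acceptance limit or sample-size calculation, so there is no stated figure to reproduce. The check is of the mechanism, under assumed values.

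**Inputs from the documents.** n = 8 volunteers (Section 1.0); 2 days each (Sections 7.0 and 11.0).

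**Assumptions.** Baseline mean 100, within-subject SD 10 (true CV 10%), between-subject SD 20% of the mean, normal errors. The condition mean is lowered to 50, 30, 20, 10 and 5% of baseline. Three error models are used:
- constant: SD = 10 at every level;
- mixed: SD = √(3² + (0.0954 × level)²), which is 10.0 at level 100;
- proportional: SD = 0.10 × level.

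**Formula.** CV = pooled within-subject SD / overall mean.

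**By hand, at level 10.**
- Constant: 10/10 = 100%.
- Mixed: √(9 + 0.91) = 3.15, and 3.15/10 = 31%.
- Proportional: 1/10 = 10%.

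**Simulation (40,000 replicates, median estimated CV).** Medians lie slightly below the true values because an SD estimated on 8 df has a median below its true value.

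| Mean, % of baseline | Constant error | Mixed error | Proportional error |
|---|---|---|---|
| 100 | 10% | 10% | 10% |
| 50 | 19% | 11% | 10% |
| 30 | 32% | 13% | 10% |
| 20 | 48% | 17% | 10% |
| 10 | 97% | 30% | 10% |
| 5 | 187% | 58% | 10% |

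Under constant error the median within-subject SD stays at about 9.6 in every row. Under mixed error it falls from 9.7 at baseline to 3.0 at level 10, so absolute repeatability improves while the CV triples.

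**A modest fall.** If the reading drops only to 60% of baseline, constant error gives 10/60 = 17%.

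**Individual CVs.** With constant error at level 10, 8.6% of simulated two-day means are zero or negative, so an individual CV has no meaning there. This depends on the normal model and would not arise for an output that cannot go below zero.

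**The formula matters.** In a separate run with SD 5 and mean 10 (true CV 50%), pooled SD over the overall mean gave a median of 48% (90% range 28 to 74%). The root mean square of individual CVs gave 57% (31 to 143%). Section 11.0 specifies neither.

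**Precision of the alternative.** The within-subject SD is √(Σd²/2n), where d is the day difference. The repeatability coefficient is 1.96 × √2 × SD = 2.77 × SD. On 8 df, the 95% CI for the SD runs from √(8/χ²₀.₉₇₅) = 0.68 to √(8/χ²₀.₀₂₅) = 1.92 times the estimate.

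**The case against.** The strongest reply is that both conditions for inflation are assumptions.

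- **Low readings.** A reader might infer that occlusion must drive the reading to zero. The documents do not say so. Section 3.0 describes the camera's ability to register physiological change as unknown. The output has no defined units; Section 4.1 pairs flow with oximetry among the secondary measures, and Section 4.2 describes spectral bands and feature extraction. Such an index may have a floor well above zero. In addition, Sections 7.0 and 9.0 allow measurement on either forearm while occluding the right brachial artery, so as written the measured arm may not be the occluded one. Those passages must be reconciled.
- **Error model.** With proportional error there is no inflation at all. The CV is then the better summary, and an SD alone would flatter the low-signal condition.
- **Reach.** Nothing suggests that reperfusion or post-capsaicin readings are near zero.
- **Consequences.** The plan ranks no conditions and sets no CV limit. A reader might also worry about CVs of change scores or of treated-minus-control contrasts, or about a plain average of two-reading CVs being biased low. Section 11.0 states none of these calculations, so they are cautions only.
- **Precision.** The wide interval on 8 df affects the SD as well as the CV, and it would narrow if the LUMC data are pooled as Section 11.0 intends. It is no argument against the CV.

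All of this stands, and it makes the point conditional. It does not remove it: the error structure is unknown, the plan has no step to examine it, and no other section supplies an absolute-scale measure.

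**Conclusion.** The point holds in conditional form. The CV is the only measure of day-to-day variability named, and occlusion readings are among those assessed. If the occlusion-phase readings are low and error does not shrink in proportion, the CV may be inflated without any loss of absolute reproducibility. For a mean at 10% of baseline and a baseline CV of about 10%, the range is about 97% (constant error), 30% (mixed error) and 10% (proportional error). The size rests wholly on the assumed mean and error model. The documents do not support saying that the occlusion CV will look poor, or that the CV is wrong for every condition. They do support saying that the CV alone cannot separate a low signal from poor repeatability.

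**What to change.** In Section 11.0, report for each condition separately (baseline, occlusion phase, reperfusion phase, post-capsaicin):

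- the within-subject SD, √(Σd²/2n), and the repeatability coefficient, 2.77 × SD, each with 95% CI;
- the mean day-2 minus day-1 difference with its CI, which would also make clear what the t-test is for if a between-day comparison is intended.

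Name the camera output, its units and the time window used for each condition. Keep the CV as a supplementary figure, with its formula stated (root-mean-square form). Interpret it only where a check of SD against mean shows that error scales with the signal and the mean is well above zero. With eight pairs per condition that check is descriptive; plotting all 4 × 8 = 32 pairs together would help.

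The cost is a change of wording, a few more lines of output and a less familiar headline figure. No extra volunteers, visits or measurements are needed.
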